7.1.2 Clinical Investigation Plan (CIP) Deviations

Full-list of protocol deviations will be reported and major violations to be excluded from Per-Protocol Analysis Set (PPAS) will be reviewed and discussed with the study team prior to run statistical analysis.

This document is electronically controlled. Printed copies are considered uncontrolled.

Confidential

7.1.3 Analysis Sets

Three analysis sets will be created for study purpose:

1. Intent-To-Treat. ITT includes all subjects:
 - who signed the informed consent
 - who satisfied the eligibility criteria
 - who began the procedure

Subjects in whom the procedure is begun but not completed will be considered “discontinued” and will be followed until discharge. These subjects will only contribute AE data intraoperatively until discharge (no additional follow-up).

2. Full Analysis Set. FAS is a subset of the ITT, restricted to subjects:
 - who signed the informed consent
 - who satisfied the eligibility criteria
 - who were operated with BiZact™ procedure successfully completed
3. Per Protocol Analysis Set. PPAS is a subset of the FAS, restricted to subjects who adhere to the protocol and do not have major protocol violation.

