8.2. Subject Enrollment

After being informed of the nature of the study, the subject will provide written informed consent that has been approved by the sponsor and the appropriate IRB/EC of the respective clinical site. A minimum of 48 subjects will be enrolled in the study at up to 3 sites with competitive enrollment not to exceed 24 subjects per site. Subjects' participation in the study will last 14 days (+3) post procedure.

A subject is considered enrolled in the study when ICF is signed, and must be followed for the full 14 days follow-up regardless of whether or not the subject received treatment with the study device.

The procedure will be performed per the institution's standard practice. Subjects will be considered for the study if they meet specific preoperative and intraoperative inclusion/exclusion criteria. The criteria for enrollment must be followed explicitly.

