9.1.2. Screening / Baseline Visit

A screening/baseline visit will be performed within 30 days up to/on the day of the scheduled procedure. Subjects will be consented prior to enrollment in the study before any procedures specific to the study are undertaken. The purpose and all aspects of the study will be explained to the subject. Subjects who

agree to study participation must sign and personally date the sponsor and an IRB/EC-approved informed consent form prior to participating in any study activities.

Once informed consent has been signed and eligibility is confirmed, the subject's demographics and medical history will be assessed to include: age, gender and weight.

- Relevant medical history will be assessed based on clinical condition categorized by category codes specified in the electronic case report form (eCRF).
- Female subjects will be assessed for childbearing potential, and if they do have childbearing potential, they will undergo a urine pregnancy test (US only). If the test is positive, they will be withdrawn from the study. If the pregnancy test is negative, these subjects should practice contraceptive methods through the course of the study. Additional urine pregnancy test will be performed on the day of surgery (US only). In Europe female subjects of childbearing potential will be asked pregnancy status. Women who respond as pregnant will not be included.

The following assessments will be performed within 30 days prior to the scheduled surgical procedure and the results recorded on the appropriate subject eCRFs:

- Verification of preoperative eligibility criteria
- Verification of surgical candidacy
- Demographic data
- Medical history, including concomitant medications and comorbidities
- Surgical history
- Medication history
- Pregnancy test, if applicable (US only)
- Concomitant medication(s)

Note: All medications will be coded using the World Health Organization (WHO) drug coding dictionary.

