11.3. Adverse Event Recording

Assessment of the occurrence of an AE will be based on changes in the subject's physical examination, laboratory results and/or signs and symptoms. Adverse events will be monitored until a subject completes the study unless the Investigator determines the event is related to the device, in which case they will be monitored until resolution if possible. Medical care will be provided, as defined in the informed consent, for any AE related to study participation. Adverse events will be collected on an AE eCRF and applicable source documentation. To the extent possible, the event to be recorded and reported is the event diagnosis as opposed to event symptoms (e.g., fever, chills, nausea and vomiting in the presence of a clinically diagnosed infection is to be reported as infection only). For the purposes of this protocol, AEs will be collected and documented in a timely manner at baseline and 0 to 14 days follow-up.

The following should not be considered an AE:

- A condition requiring a preplanned procedure unless the condition worsened since screening
- A preexisting condition found as a result of screening, unless the condition has worsened since enrollment.

All responses to the above events that require treatment beyond the institution's standard procedures will be reported as AEs.

All AEs observed during the course of this study, regardless of severity or relationship to the device will be recorded on the appropriate eCRF except for what is noted in Section 11.1.1.

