5.1 Inclusion criteria

Subjects are eligible to be enrolled in the study only if they meet **all** of the following inclusion criteria:

1. Adults (male or female) ≥ 22 years of age in United States and ≥ 18 years of age in Europe
2. Scheduled to undergo non-elective tonsillectomy
3. Signed informed consent by subject or the legally authorized representative

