7.1 Study Subjects

7.1.1 Disposition of Subjects

Screen, consented, eligible, intent-to-treat patients (ITT), operated patients (Full Analysis Set - FAS) and per-protocol patients (PP) will be summarized by frequency, as well as patients early withdrawn. Early withdrawal reasons will be presented by related reason and listed. Protocol deviations, post-operative assessment completions and length of follow-up will be reported (frequency and percentage from Full Analysis Set population).

Subjects who provide study consent, but then are determined to be ineligible prior to study procedure will be considered a screen failure and will not require additional study follow-up visits as well as subjects withdrawn due to physician decision. The reason for the screening failure will be clearly delineated.

Subjects in whom the procedure is begun but not completed will be considered "discontinued" and will be followed until discharge. These subjects will only contribute to Adverse Event data intraoperatively until discharge (no additional follow-up). They will only be part of the ITT analysis set.

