7.10 Safety Evaluation

An Adverse Event (AE) is any untoward medical occurrence, unintended disease or injury, or untoward clinical signs (including abnormal laboratory findings) in subjects, users or other persons, whether or not related to the investigational medical device.

This definition includes events related to the investigational medical device and the procedures involved. For users or other persons, this definition is restricted to events related to investigational medical devices.

Adverse Events may include but are not limited to pain, bleeding, nausea, vomiting, and headache.

AEs will be reported by frequencies and percentages of subjects by categories of AEs and by count of each AE. A listing will also be provided.

AEs will be collected and documented at baseline and 0 to 14 days follow-up. AEs will be presented globally and based on their occurrence periods: PRE-PROCEDURE, DURING PROCEDURE and POST-PROCEDURE. The MedDRA coding system will be used so as to report the AEs in the statistical tables.

Safety analysis will be run on the whole ITT population and on the FAS.

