7.10.1 Serious Adverse Event

A serious adverse event (SAE) is any AE that has:

- led to death,
- led to serious deterioration in the health of the subject that either resulted in
 - a life-threatening illness or injury, or
 - a permanent impairment of a body structure or a body function, or
 - in-patient or prolonged hospitalization, or
 - medical or surgical intervention to prevent life threatening illness or injury or permanent impairment to a body structure or a body function, or
- led to fetal distress, fetal death, or a congenital abnormality or birth defect.

NOTE: Planned hospitalization for a pre-existing condition or a procedure required by the clinical investigational plan, without serious deterioration in health, is not considered an SAE.

SAEs will be collected and documented at baseline and 0 to 14 days follow-up.

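### Every SAP analysis set is conditional on eligibility, so a treated subject found ineligible after the procedure began is in no safety frequency table; the SAP's own inclusion list is also out of date

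*Combined protocol and SAP*

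**What the plan says.** SAP 7.1.3 defines three sets: ITT, FAS and PPAS. ITT takes consented subjects "who satisfied the eligibility criteria" and in whom the procedure began. The FAS, a subset of ITT, repeats the eligibility condition and adds successful completion of the BiZact procedure. The PPAS is the part of the FAS without major violations. There is no separate safety or as-treated set.

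SAP 7.10 states: "Safety analysis will be run on the whole ITT population and on the FAS".

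SAP 7.1.1, like CIP 9.10, deals with ineligibility at one moment only. Consented subjects who are then "determined to be ineligible prior to study procedure will be considered a screen failure".

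CIP 13.3 describes the analysis population more simply, as those who enrolled and had the intended procedure. CIP 8.2 counts enrolment from the signed consent form. SAP 7.12 says that the SAP analysis matches the one planned in the CIP.

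On the criteria themselves, SAP 5.1 item 2 reads "Scheduled to undergo non-elective tonsillectomy", and item 3 also accepts consent by a legally authorized representative. Current CIP 8.3 has neither the non-elective restriction nor the representative.

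**The concern.** Safety tables should describe everyone exposed to the device. An eligibility condition on every set lets an exposed subject leave both numerator and denominator because of information that arises after exposure. In a study of about 48 subjects, one such omission can turn a reported event into a reported zero.

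The outdated list adds to this. SAP 7.1.3 makes eligibility decide who is counted but does not say whether SAP 5.1 or CIP 8.3 supplies the criteria. A programmer who follows the SAP alone would apply a restriction that the CIP no longer contains.

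**Working it through.** The study is unpowered and descriptive (CIP 13.2, SAP 6), so the plan has no calculated figure to reproduce. The check is set logic, followed by an illustration of scale.

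**Set membership as written (SAP 7.1.1, 7.1.3, 7.10)**

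| Subject | ITT | FAS | PPAS | Safety tables |
|---|---|---|---|---|
| Consented, found ineligible before the procedure | no (screen failure, untreated) | no | no | none needed |
| Eligible, procedure begun but not completed | yes | no | no | ITT |
| Eligible, BiZact procedure completed | yes | yes | if no major violation | ITT and FAS |
| Procedure begun, found ineligible afterwards | no | no | no | **none** |

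The last row follows because PPAS ⊂ FAS ⊂ ITT and ITT requires eligibility. Such a subject is not a screen failure either, since that rule applies only before the procedure.

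**Can the last row occur?** The documents leave it open.
- CIP 8.2 says: "Subjects will be considered for the study if they meet specific preoperative and intraoperative inclusion/exclusion criteria". CIP 8.3 and 8.4 label no criterion as intraoperative.
- CIP 9.1.2 allows screening on the day of surgery.
- Pregnancy is an exclusion, yet CIP 9.1.2 says: "In Europe female subjects of childbearing potential will be asked pregnancy status". A test is done only in the United States.

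**CIP against SAP.** CIP 13.3 with CIP 8.2 requires consent plus the intended procedure. SAP 7.1.3 requires consent plus eligibility plus a begun procedure. The SAP therefore adds a condition, although SAP 7.12 reports no change.

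**SAP 5.1 against CIP 8.3.** Both are current texts. The CIP version history only explains the mismatch: version 1.1 removed the representative, and version 3.0 set the regional ages and removed the non-elective restriction. The SAP has the new ages but keeps the other two items. If a share e of treated subjects were elective, applying SAP 5.1 literally would reduce each set to (1 − e) of its size. The documents do not give e.

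**Illustration of scale**

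Inputs: minimum enrolment 48 (CIP 13.2); ceiling 3 sites × 24 = 72 (CIP 8.2). CIP 12 speaks of two sites and 48 subjects, and 2 × 24 = 48, so the lower figure is the more likely one. Assumption: number treated equals number enrolled. Enrolment starts at consent, so fewer may be treated and each would then weigh slightly more.

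- Weight of one subject: 1/48 = 2.08%; 1/72 = 1.39%.
- One treated subject omitted who had the only event: 0/47 = 0.0% (exact 95% upper limit 7.5%) instead of 1/48 = 2.08% (0.05% to 11.1%). At 72 treated: 0/71 instead of 1/72.
- One omitted with an event, two events elsewhere: 2/47 = 4.26% instead of 3/48 = 6.25%.
- One omitted without an event, one event elsewhere: 1/47 = 2.13% instead of 1/48 = 2.08%.

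The chance of at least one such subject among 48 is 1 − (1 − p)^48, where p is an assumed rate of late ineligibility: 38% at p = 1%, 62% at 2%, 92% at 5%.

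**The case against.** The strongest reply is that the eligibility phrase means judged eligible before the procedure. SAP 7.1.1 lists eligible subjects as a step ahead of ITT and glosses the FAS as operated patients. SAP 7.1.2 removes major violations from the PPAS only. Under that reading a breach found later would affect the PPAS alone and the gap closes. The reading is plausible, but no sentence in the SAP states it, and the literal wording says otherwise.

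A second reply is that the events are not lost, and this largely stands. CIP 11.3 says: "All AEs observed during the course of this study, regardless of severity or relationship to the device will be recorded on the appropriate eCRF", apart from the expected observations in CIP 11.1.1. CIP 11.2 makes any ADE or SAE reportable to the sponsor. SAP 7.10.2 puts confirmed and possible device-related events in the study report with no eligibility condition. SAP 7.10 also provides an AE listing whose population is not separately stated, and SAP 7.1.2 lists all deviations. What remains is the frequency tables and their denominators.

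Three stronger inferences should be resisted:
- A reader might infer that fetal outcomes would go unseen, because SAP 7.10.1 counts as serious an event that "led to fetal distress, fetal death, or a congenital abnormality or birth defect". SAEs are collected only at baseline and from day 0 to 14, so most such outcomes would fall outside the window whichever set is used.
- A reader might infer that cases finished with another device are excluded from the FAS, because successful completion is not defined. SAP 7.7 summarises surgical procedure data, including alternative-device use, on the FAS, which implies that they stay in.
- A reader might infer that elective patients were kept out of the study. Enrolment follows CIP 8.3, so SAP 5.1 is a text error. Its representative wording is broader than the CIP and cannot remove anyone from a set.

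**Conclusion.** The point holds on the text and should be fixed before analysis. As written, a consented, device-treated subject found ineligible after the procedure began belongs to none of the three sets and to neither safety population, a condition that CIP 13.3 does not impose. SAP 5.1 is out of date, and 7.1.3 does not say which list governs.

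The consequence is limited to frequency tables and denominators. No actual effect can be sized, because the documents give neither a rate of late ineligibility nor a share of elective cases. One subject weighs 2.1 percentage points at 48 treated and 1.4 at 72. The conclusion rests on the literal meaning of the eligibility condition; a stated rule that eligibility is judged before the procedure would remove the main gap.

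**What to change.** 1. In SAP 7.1.3 add a safety set: all consented subjects in whom the BiZact procedure was begun, regardless of eligibility. Run SAP 7.10 on it. List treated subjects found ineligible, with the criterion concerned, and handle eligibility breaches as deviations that affect the PPAS.
2. Replace SAP 5.1 items 2 and 3 with the CIP 8.3 text, and have SAP 7.1.3 cite the CIP criteria.

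The cost of both is SAP text, one set definition and one listing.

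Two minor wording points can go with them. State in SAP 7.1.3 that cases finished with another device are in the FAS, as SAP 7.7 implies. Reconcile CIP 8.2, which asks for full 14-day follow-up whether or not the device was used, with CIP 9.10 and SAP 7.1.1, which follow discontinued subjects only to discharge. This last item touches CIP text and may need an amendment with ethics review under CIP 15.6. The other changes do not depend on it.

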Speech problems	HNSP	3	3	16, 23, 24
Trouble with social eating	HNSO	4	3	19-22
Trouble with social contact	HNSC	5	3	18, 25-28
Less sexuality	HNSX	2	3	29,30
Teeth	HNTE	1	3	9
Opening mouth	HNOM	1	3	10
Dry mouth	HNDR	1	3	11
Sticky saliva	HNSS	1	3	12
Coughing	HNCO	1	3	15
Felt ill	HNFI	1	3	17
Pain killers	HNPk	1	1	31
Nutritional supplements	HNNu	1	1	32
Feeding tube	HNFE	1	1	33
Weight loss	HNWL	1	1	34
Weight gain	HNWG	1	1	35

* Item range is the difference between the possible maximum and the minimum response to individual items.

Example:

Pain

$$\text{RawScore} = (Q1 + Q2 + Q3 + Q4)/4$$

$$\text{Pain Score} = \{(\text{RawScore}-1)/\text{Item range}\} * 100$$

Questions scores

Not at all = 1

No = 1

A little = 2

Yes = 2

Quite a bit = 3

Very much = 4

This document is electronically controlled. Printed copies are considered uncontrolled.

Confidential

- The incidence of patients having a post-operative hemorrhage, primary and secondary bleeding, and post-operative readmission along the follow-up will be assessed.
- Intra-operative bleeding, irrigant volumes and operative time will be calculated (counts, means, standard deviations, medians, minimum and maximum).

Secondary objectives will be run on both FAS and PPAS.

This document is electronically controlled. Printed copies are considered uncontrolled.

Confidential

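### SAP 5.1 keeps a non-elective inclusion criterion that CIP 8.3 does not have, and the set definitions would carry it into every analysis set; the completed-procedure rule for the FAS is a smaller gap in the hemorrhage tables

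*Combined protocol and SAP*

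**What the plan says.** **Eligibility.** SAP 7.1.3 makes meeting the eligibility criteria a condition of both the ITT set and the FAS, and defines the PPAS as a subset of the FAS. SAP 5.1 item 2 asks for a non-elective tonsillectomy, and item 3 accepts consent from a legally authorized representative. Current CIP 8.3 asks only for a scheduled tonsillectomy and for the subject's own consent. The SAP text appears twice in the file, with the same wording.

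**Completion.** SAP 7.1.3 limits the FAS to subjects "who were operated with BiZact™ procedure successfully completed". Of subjects whose procedure was begun but not completed, SAP 7.1.1 says "They will only be part of the ITT analysis set"; they give adverse-event data until discharge and have no further follow-up. Post-operative hemorrhage falls under SAP 7.9.2, which states "Secondary objectives will be run on both FAS and PPAS". For adverse events, SAP 7.10 states "Safety analysis will be run on the whole ITT population and on the FAS".

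**Follow-up.** Under SAP 7.1.1, "length of follow-up will be reported (frequency and percentage from Full Analysis Set population"). CIP 8.2 requires 14 days of follow-up for every enrolled subject, treated with the device or not. CIP 9.10 ends follow-up of non-completers at discharge.

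**The concern.** The SAP does not say which eligibility criteria SAP 7.1.3 means, so the natural reading is its own section 5.1. A programmer who follows it would remove every elective case, although the CIP allows those subjects to enroll. The loss would affect the ITT set, the FAS and the PPAS alike, and so every table in the report.

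The FAS rule raises a separate question. Completion is known only during surgery, so the hemorrhage tables are restricted by an intra-operative outcome. A procedure that could not be finished is one where a reader would want to know about bleeding. Primary bleeding runs to 24 hours (SAP 4.2) and secondary bleeding beyond that, so a non-completer who is discharged early is not observed through either window. Because length of follow-up is summarized on the FAS only, the shortfall is not shown where it occurs.

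**Working it through.** The plan has no powered figure to reproduce: 48 is a pre-defined minimum (CIP 13.2). The check compares texts and then illustrates size. The documents give no elective, non-completion or bleed rate, so those inputs are assumptions.

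**1. Eligibility text side by side**

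| Item | CIP | SAP | Effect on the sets |
|---|---|---|---|
| Type of procedure | 8.3: any scheduled tonsillectomy | 5.1: non-elective only | elective cases leave all three sets |
| Consent | 8.3: subject | 5.1: subject or representative | more permissive, removes nobody |
| Exclusion of elective cases | 8.4: none | 5.2: none | the two agree |

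Only inclusion item 2 narrows the sets.

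**2. Size if item 2 is applied literally.** With elective share s, n = 48(1 − s). The half-width of a 95% interval for a daily mean VAS is t(0.975, n − 1) × SD/√n, with SD assumed at 2.0 or 2.5. The one-sided 95% upper bound for an event seen in nobody is 1 − 0.05^(1/n).

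| s | n | Half-width, SD 2.0 | Half-width, SD 2.5 | Zero-event upper bound |
|---|---|---|---|---|
| 0% | 48 | 0.58 | 0.73 | 6.1% |
| 25% | 36 | 0.68 | 0.85 | 8.0% |
| 50% | 24 | 0.84 | 1.06 | 11.7% |
| 75% | 12 | 1.27 | 1.59 | 22.1% |

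**3. Hemorrhage on the FAS against all who began.** Let N subjects begin, k not complete, 3 completers bleed, and x of the k bleed. The FAS rate is 3/(N − k). The rate over all who began is (3 + x)/N, with x from 0 to k.

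| N | k | FAS | All who began, x = 0 to k |
|---|---|---|---|
| 48 | 0 | 6.25% | 6.25% |
| 48 | 1 | 3/47 = 6.4% | 6.25% to 8.3% |
| 48 | 3 | 3/45 = 6.7% | 6.25% to 12.5% |
| 48 | 5 | 3/43 = 7.0% | 6.25% to 16.7% |
| 72 (3 sites × 24) | 3 | 3/69 = 4.3% | 4.2% to 8.3% |
| 72 | 5 | 3/67 = 4.5% | 4.2% to 11.1% |

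Each range lies inside the Agresti-Coull 95% interval of the matching FAS rate: 1.6% to 18.5% for 3/45, 1.7% to 19.3% for 3/43, and 1.0% to 12.9% for 3/67. When no non-completer bleeds, the FAS rate is slightly the higher of the two.

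The chance of at least one non-completer among 48 is 1 − (1 − p)^48. For assumed p of 1%, 2%, 5% and 10% it is 38%, 62%, 91% and 99%.

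**4. Choice of denominator.** A tempting repair is to count, for primary bleeding, subjects who were followed to 24 hours or had an event. That keeps an early-discharged subject only if the subject bled. Take 45 completers with 3 bleeds and 3 non-completers, all discharged before 24 hours, one with a bleed. The rule gives 4/46 = 8.7% overall and 1/1 among non-completers, against 1/3 recorded. Recorded events over all who began give 4/48 = 8.3%. If the two unobserved subjects are both counted as bleeding, the bound is 6/48 = 12.5%.

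**The case against.** On eligibility, the fair reply is that CIP criteria govern enrollment, that SAP 5.2 already agrees with CIP 8.4, and that a sensible statistician would not discard correctly enrolled subjects over one leftover word. That makes the harm avoidable. It does not make the text right, because SAP 7.1.3 does not point to the CIP.

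On the FAS, the reply is stronger:

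- CIP 13.3 bases the analyses on enrolled subjects who undergo the planned procedure, so the FAS follows the CIP.
- SAP 7.1.1 reports the ITT and FAS counts, so the number of non-completers is already visible, and under SAP 7.1.2 "Full-list of protocol deviations will be reported".
- SAP 7.10 says "Adverse Events may include but are not limited to pain, bleeding, nausea, vomiting, and headache", and plans a listing, so a non-completer's bleed before discharge is reported.
- Safety also runs on the FAS, so any dilution of the ITT rate can be seen beside an undiluted one. With 3 post-discharge events, N = 48 and k = 3, the dilution is 3/45 − 3/48 = 0.42 percentage points.
- CIP 9.10 can be read as the specific rule for non-completers and CIP 8.2 as the general one.

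All of this stands, and it is why the FAS point is minor. What remains is that new events after discharge are not collected for non-completers, no hemorrhage table covers everyone who began, and CIP 8.2 contains no reference to the exception in 9.10.

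The size illustration has its own limits. Enrollment is counted from consent, so fewer than 48 may begin the procedure, and 72 needs a third site while CIP 12 and Appendix C describe two.

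**Conclusion.** The eligibility mismatch is a conflict between two current texts. Applied literally, SAP 5.1 item 2 removes elective cases from all three sets. The loss cannot be sized from the documents; 36, 24 or 12 of 48 are outcomes of assumed shares. It should be corrected before the analysis sets are built.

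The FAS point is minor. The hemorrhage tables omit non-completers, but under the assumed counts the effect stays within the sampling uncertainty of the FAS rate, and it is zero if everyone completes.

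A reader might infer more, and the documents do not support it:

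- *That the SAP deliberately limits the analysis to non-elective cases.* SAP 5.2 has no elective exclusion, and SAP 7.12 says the analysis corresponds to the CIP.
- *That bleeding in non-completers is hidden.* Recorded bleeds reach the ITT adverse-event tables and the listing.
- *That the FAS rate is biased downward.* That holds only if non-completers bleed more often than completers, and no figure bears on it.
- *That leaving out non-completers shifts mean VAS.* They give no VAS data and nothing is imputed (SAP 7.4).
- *That cases finished with another device are excluded from the FAS.* CIP 9.1.3 allows another device when medically needed, SAP 7.1.1 describes the set as "operated patients (Full Analysis Set - FAS"), and SAP 7.7 summarizes alternative devices on it. Inclusion is the better reading, but SAP 7.1.3 can be read the other way.

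**What to change.** 1. Replace SAP 5.1 items 2 and 3 with the CIP 8.3 wording, and have SAP 7.1.3 cite CIP 8.3 and 8.4. Make the edits in both copies of the SAP text.
2. State in SAP 7.1.3 that a tonsillectomy completed with another device, as CIP 9.1.3 permits, is in the FAS.
3. Add a supportive ITT hemorrhage row: recorded events over all who began the procedure, with the number of non-completers not observed through the primary and secondary windows. If wanted, add bounds that count the unobserved as none or all bleeding. Do not use a denominator that keeps early-discharged subjects only if they bled.
4. Report length of follow-up on the ITT set as well as the FAS.
5. Reconcile CIP 8.2 and 9.10 on follow-up of non-completers. This review does not choose the rule.

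Items 1 to 4 cost SAP wording and one extra table, and may give slightly less favorable rates. Item 5 may need a CIP amendment, which under CIP 15.6 means sponsor, IRB/EC and any applicable regulatory approval, plus site training.
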